## 1. Abstract

Health behaviors are major, modifiable risk factors for the development and progression of chronic diseases, which account for a large proportion of all deaths in the US and contribute to disparities in premature mortality based on both income and race. There is substantial evidence, for example, that behaviors like smoking, physical inactivity, and unhealthy diet are associated with an increased risk of cardiovascular disease (CVD), as are modifiable factors such as blood pressure, cholesterol, body mass index, and fasting glucose. A growing body of research suggests that poverty may affect health behaviors through financial and psychological pathways. However, few studies have rigorously examined the effects of poverty alleviation interventions on health behaviors, particularly among individuals at high risk for CVD. Even fewer studies have examined potential psychological mechanisms by which anti-poverty interventions might influence health behavior. This pilot project will examine the effect of unconditional cash transfers, an economic intervention that is gaining traction among policymakers, on risk factors for CVD and other chronic diseases. The project will focus on low-income adults in Philadelphia who have at least one health risk factor for CVD (type 2 diabetes/pre-diabetes and/or hypertension) and examine whether short-term, unconditional cash transfer payments result in changes in objective and self-reported health outcomes. Our second aim will examine potential psychological mechanisms through which the cash transfer intervention may affect study participants' behavior, including mental health, psychosocial stress, bandwidth, and future orientation. Our third aim will use qualitative methods to understand participants' experiences with this study. The project activities will include developing and testing the cash transfer intervention (Stage 1) as well as basic science analysis of mechanisms of change (Stage 0).

## 2. Objectives and Aims

We will conduct a pilot trial of a short-term unconditional cash transfer provision and evaluate its effects on health behaviors and outcomes. Our overall goals are to assess the feasibility and acceptability of the intervention, to measure key outcomes that may be affected by the intervention, and to identify plausible intervention effect sizes that can be used to conduct a larger trial. Our specific aims are:

**Aim 1: Determine the effect of an unconditional cash transfer provision on specific health behaviors that influence CVD risk, financial outcomes, and health risk factors that are directly related to insufficient financial resources (food and utility security) (Stage 1, create and test new behavioral interventions).** In partnership with Penn Family Care clinics, we will identify potential participants who may be eligible for the study. We will then enroll and randomize about 100 low-income adults with either hypertension or pre-diabetes/diabetes to either: 1) usual care or 2) eight cash transfer payments of \$125 every two weeks (for a total of \$1000 over 4 months). At baseline and at 3 months (before the eighth payment, to minimize the influence the intervention ending has on follow up measures), we will assess our **primary outcomes** of health behaviors (health care utilization, medication adherence, smoking behavior, and alcohol use), financial outcomes (health care expenditures, financial stress) and health risk factors associated with insufficient financial resources (food and utility insecurity). We will also examine secondary health outcomes including self-reported health-related quality of life, and objectively measured body mass index and blood pressure.

**Aim 2: Assess potential psychological mechanisms through which the intervention influences cardiovascular health (Stage 0, research on mechanisms of change).** At baseline and 3 months, we will measure several factors that are hypothesized to affect participants' health behaviors and cardiovascular health, including their mental health, psychosocial stress, mental bandwidth, and time preferences.

**Aim 3: Conduct in-depth qualitative interviews with research participants to better understand intervention effects and mechanisms and experiences with the study.** Our primary outcomes will be a series of themes related to participants' experience as a part of a guaranteed basic income study and perceptions of how the study did or did not help support their physical and mental health.

### **3. Background**

Health behaviors are major, modifiable risk factors for the development and progression of chronic diseases, which account for a large proportion of all deaths in the US and contribute to disparities in premature mortality based on both income and race. There is substantial evidence, for example, that behaviors like smoking, physical activity, and diet are associated with an increased risk of cardiovascular disease (CVD), as are modifiable factors such as blood pressure, cholesterol, body mass index, and fasting glucose. Although some interventions to target these risk factors for CVD have had considerable success –e.g., tobacco policies like taxes and clean indoor air laws –many adults remain at high risk for CVD and large racial and economic disparities in chronic disease risk continue to persist. This is in part because few policies have addressed poverty as a fundamental driver of health.

**A growing body of research suggests that poverty affects human behavior through financial and psychological mechanisms.** In addition to the readily apparent economic pathways by which poverty may reduce one's engagement in health-promoting behaviors (e.g., inability to access or afford healthy food or preventive health services), recent studies indicate that poverty also has negative psychological consequences. In particular, poverty and chronic indebtedness can increase stress and consume mental bandwidth. Intriguingly for the study of health behavior, recent research suggests that poverty may result in less future-oriented decision-making. Despite growing interest in the psychological consequences of poverty, however, few studies have rigorously examined the effects of poverty on health behaviors and the mechanisms by which poverty alleviation might influence behavior. Determining the impact of poverty alleviation interventions on health behaviors and CVD risk – and the channels through which these effects operate – will fill important scientific and policy gaps.

**Guaranteed income programs that provide recurring monthly payments of \$500 or more are being piloted in several cities in the US, and the use of direct cash transfers has also been adopted at the national level (e.g., direct payments in American Rescue Plan).** While emerging evidence suggests that cash transfers improve socio-economic outcomes, there are significant evidence gaps as to whether they also improve health behaviors, reduce chronic disease risk factors, and lessen socio-economic disparities in chronic disease risk. The project activities will include developing and testing the cash transfer intervention (Stage 1) as well as basic science analysis of mechanisms of change (Stage 0). Findings from the project will provide suggestive evidence of whether bold economic interventions that address the economic and psychological consequences of poverty have the potential to promote health behavior. If

successful, the findings will inform a larger-scale efficacy trial that will examine whether guaranteed income interventions reduce CVD risk among low-income adults.

#### **4. Study Design**

We will conduct a two-arm randomized controlled trial to examine the feasibility, acceptability, and likely effect of an unconditional cash transfer intervention on self-reported and objectively measured health behaviors and outcomes among low-income adults. A detailed outline of study design can be found in Study Procedures.

##### **4.1. Study Duration**

Randomized-controlled trial duration: The duration of study participation will be 4 months after enrollment. We expect the total duration of the study to last 8 months given the expected time to recruit and enroll all participants. We will aim to recruit participants from March 2023 through July 2023. We estimate that the study will be completed by October 2023.

Qualitative interview duration: Participants' engagement in this part of the study is expected to last approximately 60 minutes.

##### **4.2. Target Population**

The study population will be comprised of primary care patients at Penn Family Care in West Philadelphia. We will enroll a total of 100 participants — 50 will be assigned to the usual care arm (Arm 1) and 50 will be in the intervention arm (Arm 2).

Participants enrolled by Penn Researchers: 100

Participants enrolled by Collaborating Researchers: 0

##### **4.3. Inclusion Criteria:**

- Age 18 years or greater
- Pennsylvania Medicaid enrollee
- At least one clinic visit at Penn Family Care within six months of the start of the study
- Diagnosis of pre-diabetes/diabetes and/or hypertension
- Actively prescribed a medication for diabetes or hypertension
- Regular resident of the Philadelphia metro area without plans to leave in the next 6 months

##### **4.4. Exclusion Criteria:**

- Does not meet all of the inclusion criteria
- Unable to provide consent
- Non-English speaker
- Cognitive impairment, per PIs discretion
- Cannot be in the same household as another enrolled study participant

##### **4.5. Populations vulnerable to undue influence or coercion**

All participants in this study will receive the usual standard clinical care. Participants will be informed that this study is voluntary, and they are free to withdraw at any time.

#### **5. Study Procedures**

## 5.1. Procedures

Clearance was obtained from Family Medicine Research Committee indicating that we will not need to inform physicians at Penn Family Care that their patients will be contacted for recruitment. A list of potentially eligible participants will then be generated by [name] (PI, UPHS Physician who has completed SlicerDicer research training through Penn KnowledgeLink) through the electronic medical record based on the inclusion criteria using EPIC's SlicerDicer tool. These potentially eligible participants will be routed from SlicerDicer to an EPIC Report for access to identifiable information after entering the IRB-approved protocol number.

- The list of variables that will be pulled include:

- MRN
- Patient name
- DOB
- Age
- Sex
- PCP
- Pt Portal Status
- Last Visit Date
- Last Visit Provider
- Last PCP visit
- Next PCP visit
- Payor
- Patient Type
- Active FYIs
- PCP Department
- Zip Code
- Rsch.Cntct.Pref
- Phone

Study staff will not have any involvement in the clinical care of potential participants. Recruitment will be done using a batched approach starting with 1) MyPennMedicine messages, followed by 2) Text messages, and finally 3) QR Codes in the clinic. Potentially eligible patients will first be contacted using a MyPennMedicine message with a REDCap survey link to our study interest form. For participants who respond to the survey interest form, the variables phone, patient name, DOB, and last visit date will be added to our REDCap project. Participants that do not complete an interest form via MyPennMedicine will be sent a text asking if they'd like to complete the online interest form via text, or if they would like to receive a call by research study staff with additional information about the study. Research staff will follow-up with a phone call for those who did not complete the interest form via text and ask if they'd like to complete the interest form over the phone. Research staff will be able to confirm the participant's identity over the phone by using name and DOB. Survey interest forms will be matched with the eligible EHR list pulled from SlicerDicer to confirm eligibility. Eligible participants will be contacted by phone to confirm interest in the study and schedule the baseline appointment. Study staff will describe the intervention and inform potential participants that the cash transfers may lead to SSI slightly overpaying them and asking for money back, which they can ask SSA to waive. Participants will also be informed that our team has received a notice from the state of Pennsylvania that the study payments will not count as income for state programs such as SNAP, TANF, and Medicaid, so their eligibility for these programs **will not** be affected by their participation. Eligible and interested potential participants will then be scheduled for an in-person baseline visit with study staff, where informed

consent will be obtained (see consent procedures, below, for additional details). The in-person visits will take place at [name] at the Psychology of Eating and Consumer Health Lab at the University of Pennsylvania (PI: [name]).

Written consent will be obtained from participants during the initial in-person visit, prior to the study session. A single consent will be used for all study activities except the qualitative interviews, which will involve a separate consent process. The following data will be collected during the baseline assessment:

- Survey data – Study staff will administer an in-person REDCap survey that will capture the following:
  - Sociodemographics including age, sex, gender, address of residence, zipcode, race, ethnicity, sexual orientation, marital status, schooling attainment
  - Economic data including work, income sources (including government programs such as SNAP, TANF, and WIC), and total household income
  - Food security assessment in accordance with USDA methodology
  - Utility security (Home Energy Insecurity Scale)
  - Housing data including living situation, household composition, and housing security
  - Health-Related Quality of Life (CDC HRQOL-4)
  - Health Spending
  - Tobacco use (CDS-5)
  - Alcohol use (AUDIT-C)
  - Medication Adherence (ARMS)
  - Kessler Psychological Distress Scale (K6+)
  - CFPB Financial Stress Scale
  - Perceived Stress Scale (short form)
  - State Trait Anxiety Inventory (State questions only)
  - Time preference measures
  - Acceptability of Intervention Measure (follow up only)
- Electronic Medical Record
  - Number of ED/Hospital visits in last 3 months
  - Number of non-ED visits in last 3 months
  - Number of chronic medications
  - Chronic medical conditions (problem list)
- Objective data (measured by study staff and entered directly into REDCap)
  - Height
  - Weight
  - Blood pressure
- Cognitive testing (mental bandwidth)
  - Psychomotor Vigilance Task (PVT)
    - PVT is a computer-based task that assesses attentional vigilance, asking participants to press a button when a stimulus appears on a screen and measuring reaction time and accuracy
    - For this computer-based task, no identifying information is entered, and immediately upon completion the program puts out the relevant data (e.g. reaction time, accuracy), which will be directly and immediately entered into REDCap by study staff
- W9 and C2
  - W9 (including SSN) and C2 will be collected for all participants . These will be completed by paper and stored in a secure location only accessible by study

personnel. At the end of the study, W9 forms will be scanned and sent via SecureShare to [name] to be logged into the Greenphire W-9 Database. Once scanned, paper copies will be shredded.

At the end of the baseline assessment, participants will be randomized using a permuted block technique with block size of 4 to either usual care (Arm 1) or to the unconditional cash transfer intervention (Arm 2). Participants in Arm 2 will receive an unconditional cash transfer of \$125 every 2 weeks for 8 payments via ClinCard, for a total of \$1000. In addition, 16 participants will also be randomly selected to receive a blood pressure cuff to take home. Of these 16, 8 will be blood pressure cuffs that wirelessly transmit readings to an app on their mobile phone. Participants that receive a blood pressure cuff will be asked to take a blood pressure reading weekly for the duration of their enrollment period, and record their reading via a REDCap survey link sent by text. Those receiving a wireless blood pressure cuff will transmit their readings wirelessly, as well as record their reading in the weekly REDCap survey link. The goal of this procedure is to pilot test the feasibility of this technology and approach for a future, larger study.

All participants will be asked to return for an in-person assessment at month 3. This assessment will include all elements of the baseline assessment. Additionally, intervention participants will complete the Acceptability of Intervention Measure and be asked a survey question about how the cash transfer was used. Participants randomized to receive a blood pressure cuff will also be asked to complete a short survey regarding their acceptability and use of a blood pressure cuff at home.

Via ClinCard, all participants will receive \$25 compensation for completing the baseline assessment, and \$50 for completing the follow-up assessment. Participants providing at-home blood pressure readings will receive an additional \$3 per reading (maximum \$3 per week, \$48 total).

**Qualitative interview procedures:** During the 3-month study visit, up to 35 interested study participants (25 intervention, 10 control) will be selected to participate in a follow up qualitative interview to better understand their experience in the study, including the mechanisms by which poverty and cash transfers may affect health behaviors (see attached in-depth interview guides). Participant interest will be obtained during the baseline visit and documented in a secure REDCap database. Once participant interest is confirmed, research staff will randomly select 35 interested participants and schedule their interview at the end of their 3-month study visit through Outlook using only their Record ID. A copy of the verbal informed consent form will be provided at the time of this visit, so they have time to review prior to the interview. Once interview appointments are scheduled, participants will receive a reminder text the week prior and the day before their interview to remind them about the time/date of their interview.

The qualitative research interviewer will call the research participants at the phone number that they provide our research team in REDCap. Prior to conducting the qualitative interviews, the research interviewer will run participants through a verbal consent process (a copy of the verbal consent script has been attached to this submission). Verbal consent will be documented in a secure REDCap database.

The research interviewer will then conduct an audio-recorded qualitative interview with research participants using the Guaranteed Income Control and Intervention Interview Guide (attached to this submission). Upon completion of the interviews, the qualitative interviewer will transcribe the interviews and upload transcription notes to a secure data server. The digitally recorded

interviews will then be professionally transcribed and loaded into NVivo software for data management and analysis.

Our scripted Mosio text messages have been attached to this submission. Participants will be compensated \$35 for completing the in-depth interviews.

Baseline and 3-month study visits will occur in-person in a private room at [name] at the Psychology of Eating and Consumer Health Lab at the University of Pennsylvania (PI: [name]).

There will be no subject follow-up after the 3-month study visit and qualitative interview.

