### **9.2 Subject Confidentiality**

[name] is a UPHS physician with access to SlicerDicer who has completed SlicerDicer research training through Penn Knowledge Link. He will be generating the eligibility dataset on SlicerDicer and exporting the data to an EPIC Report using the IRB-approved protocol number. He will send recruitment MyPennMedicine messages directly through EPIC to potential participants on this report. He will also download this dataset as a .csv file onto a UPHS Computer, and this dataset will be uploaded onto REDCap for the team to use during follow-up of people completing the interest form, to assess for eligibility.

Data will be entered directly on encrypted University of Pennsylvania computers into the web-based password-protected REDCap database. Collected Protected Health Information (PHI) will include the following: Name, address (for the purpose of ClinCard compensation), zip code, telephone number, and social security number (for the purpose of ClinCard compensation). Participants will automatically be assigned a study ID through the REDCap system. When records are complete, data will be downloaded from the web-based system with the generated study ID. Protected Health Information (PHI) will be delinked from the data and inaccessible to all study staff aside from the Investigators. At the end of the study, a list of MRNs for consented study participants will be submitted in a DACS request to obtain their active problem list, medications history, and visits (office, ED, hospital) 3 months before and after their study start date. This limited dataset will be used for analysis and will be maintained on an encrypted and password-protected University of Pennsylvania server accessible only to the Investigators.

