## **Dataset**

**Sample:** Survey and measurement data from 100 participants at baseline and 3-month follow-up in a two-arm randomized controlled trial (50 in control, 50 in intervention). Participants are adult patients at UPenn Family Care on Medicaid with either a prediabetes, diabetes, or hypertension diagnosis who have received care there in the past 6 months, live in the greater Philadelphia area, and are actively prescribed oral medication for diabetes or hypertension. Participants will be recruited using UPenn Family Clinic EHRs. Initial interest data will be collected via a REDCap online survey. Most other data will be collected through REDCap surveys completed in-person at the baseline and 3-month visits. Participants' blood pressure and height and weight measurements will also be taken at these visits, and participants will complete a psychomotor vigilance task as well as a behavioral snack choice. 16 participants will receive a blood pressure cuff to take home and send measurements weekly (for 16 weeks; 8 control, 8 intervention; half of each group will transmit wirelessly, the other half won't). These participants will be texted REDCap surveys to fill out weekly with blood pressure measurements. Finally, participant EHR data will be pulled for the 3 months prior to their baseline measurement and 3 months after matched on name and birthdate.

**Intervention:** In the unconditional cash transfer intervention, participants will receive \$125 every 2 weeks for 8 payments via ClinCard, for a total of \$1000.

**Primary Outcome:** Our 8 primary outcomes for this pilot study are:

1. food security (3-category, US Dept of Agriculture) (Aim 1)
2. utility security (5-category; Home Energy Insecurity Scale) (Aim 1)
3. financial well-being scale (0-100, Consumer Financial Protection Bureau Financial Well-Being) (Aim 1)
4. Perceived Stress Scale (0-16, short form) (Aim 2)
5. state anxiety scale from the State Trait Anxiety Inventory (standardized score as per the manual) (Aim 2)
6. number of lapses in the Psychomotor Vigilance Task (Aim 2)
7. health care expenditures on medications (raw dollars) (Aim 1)
8. adherence to medication refills subscale (4-16; Adherence to Refills and Medications Scale (ARMS)) (Aim 1)

Aim 1 = Specific health behaviors

Aim 2 = Potential psychological mechanisms

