## Data Analysis

**Primary Statistical Methods & Software:** All outcomes will be analyzed at the participant level. Analyses will employ population-averaged marginal models estimated by Generalized Estimating Equations (GEE) to account for correlations among the within-person baseline and follow-up measurements. Marginal models estimated by GEE are advantageous for their population-level interpretation and robustness of estimated effects to the assumed correlation structure among repeated measurements (meaning unbiased estimates of the effect of the behavioral intervention will be obtained whether or not the correlation among repeated measurements within a participant is modeled correctly). Clusters will be defined at the level of the participant for all analyses, and independent working correlation will be assumed. Linear models will be used for continuous outcomes and logistic models for categorical or ordinal outcomes. Analyses will be conducted using Stata.

Models will include intervention, measurement timepoint, and the interaction of intervention and measurement timepoint as categorical variables. The primary analysis testing the effectiveness of the cash transfers compared to the control arm will be evaluated by the test of the null hypothesis that the intervention-measurement timepoint interaction coefficient is 0, denoting no difference in the change in respective outcomes from baseline to month 3 between intervention and control. The Holm procedure at a family-wise error rate of 0.05 will be used to account for multiple comparisons in testing differences in the 8 primary outcomes between the two groups.

**Exclusion Criteria & Restrictions:** Physician co-investigators will clarify any values that appear out of range (e.g., biologically implausible values) prior to excluding any data. Any data that are excluded will be done prior to re-matching participants to study arm.

**Assumption Checking & Data Cleaning:** Data will be descriptively summarized and evaluated for quality prior to analyses. Means and standard deviations will be used to characterize continuous variables such as weight and blood pressure, and frequencies and percentages will be used to describe categorical variables. Medians and interquartile ranges will be reported for continuous variables that exhibit skewness. Data will be descriptively summarized overall and by study arm.

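### ED and non-ED visit counts are tested as change from a 3-month records count with no baseline adjustment; using the pre-baseline counts as covariates would be more precise, most clearly for ED visits

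*Protocol*

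**What the plan says.** Protocol section 5.1 lists two record-based counts at baseline: "Number of ED/Hospital visits in last 3 months" and "Number of non-ED visits in last 3 months". Section 9.2 describes how the records are obtained: "At the end of the study, a list of MRNs for consented study participants will be submitted in a DACS request", covering "visits (office, ED, hospital) 3 months before and after their study start date". The SAP (Dataset) uses the same windows: "participant EHR data will be pulled for the 3 months prior to their baseline measurement and 3 months after".

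Both documents specify a GEE with arm, timepoint and their interaction under independence working correlation. The tested null is a zero interaction, "denoting no difference in the change in respective outcomes from baseline to month 3 between intervention and control". Models are linear for continuous outcomes and logistic for categorical or ordinal ones; no count model is named.

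Baseline covariates enter only in a sensitivity analysis, and only if they differ between arms at the 0.05 level. The SAP's covariate list does not include earlier visit counts.

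ED and non-ED visits are two of the nine primary outcomes in Protocol section 7. In the SAP they are secondary outcomes 1 and 2, outside its Holm family of eight.

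**The concern.** A count over one quarter reflects both a person's underlying rate and chance. If visits are rare, chance dominates. A change score subtracts the whole baseline count, chance included, so the arm comparison carries two doses of noise. Baseline adjustment instead weights the earlier count by how well it predicts the later one.

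At stake is the precision of two outcomes with 50 people per arm, in a pilot meant to supply plausible effect sizes for a larger trial. Unlike the survey measures, the pre-baseline visit count comes from a retrospective records request, so improving it adds no visit and no burden for participants.

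**Working it through.** **What the planned test estimates.** With complete data, the linear GEE interaction is the difference between arms in mean change. One simulated data set gave 0.14 with SE 0.159 by both routes.

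**Inputs.** From the documents: 3 months before, 3 months after, 50 per arm. The documents give no visit mean, variance or correlation, so there is no planned figure to reproduce. Assumed: visits are Poisson around a personal rate that varies between people.
- *m*: mean visits per 3 months. ED 0.2-0.5; non-ED 1.5-4.
- *k*: between-person variance of the rate divided by m². ED 1-3; non-ED 1-2.
- *r*: correlation of a person's rate from one quarter to the next, falling as r, r², r³ and so on. Values 1 (stable), 0.9 and 0.8.

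**Formulas, variance per person.**
- Follow-up count alone: V = m + k·m².
- Pre-post correlation: ρ = r·k·m² / V.
- Planned change contrast: 2V(1 − ρ).
- 3-month count as covariate: V(1 − ρ²).
- Two covariates (last 3 months; earlier 9 months): V − c′S⁻¹c, where c holds their covariances with follow-up and S is their covariance matrix.

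**When subtraction costs precision.** The chance share of a 3-month count is m / V = 1/(1 + mk), which exceeds one half when mk < 1. Change is less precise than ignoring baseline when ρ < 0.5. With stable rates that is again mk < 1. With r = 0.8 it is mk < 1/(2 × 0.8 − 1) = 1.67.

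**Worked case: ED, m = 0.3, k = 2, stable.** V = 0.3 + 2 × 0.09 = 0.48 and ρ = 0.18/0.48 = 0.375.
- Planned: 2 × 0.48 × 0.625 = 0.600, which is 25% above 0.48.
- 3-month covariate: 0.48 × (1 − 0.1406) = 0.412.
- Adding the earlier 9 months: with stable rates this equals one 12-month covariate, whose variance is 0.3/4 + 0.18 = 0.255. So 0.48 − 0.18²/0.255 = 0.353.

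The total fall is 0.247, of which 0.188 (76%) comes from adjustment alone.

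| m, k, r | Follow-up only | Planned change | 3-month covariate | Two covariates | Pooled 12-month rate as baseline row |
|---|---|---|---|---|---|
| 0.3, 1, 1 | 0.390 | 0.600 | 0.369 | 0.341 | 0.375 |
| 0.3, 2, 1 | 0.480 | 0.600 | 0.412 | 0.353 | 0.375 |
| 0.3, 2, 0.8 | 0.480 | 0.672 | 0.437 | 0.421 | 0.482 |
| 0.5, 3, 1 | 1.250 | 1.000 | 0.800 | 0.607 | 0.625 |
| 2, 1, 1 | 6.00 | 4.00 | 3.33 | 2.44 | 2.50 |
| 2, 1, 0.8 | 6.00 | 5.60 | 4.29 | 4.13 | 4.87 |
| 4, 2, 0.8 | 36.0 | 20.8 | 17.8 | 17.6 | 24.0 |

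**Ranges over the assumed values.**
- ED, two covariates against planned: ratio 0.56-0.71, or 29-44% lower variance. Adding the longer window to the 3-month covariate cuts the adjusted variance by 5-24% if rates are stable, 3-10% at r = 0.9 and 1-4% at r = 0.8.
- Non-ED, two covariates against planned: ratio 0.61-0.86, or 14-39% lower.
- Pooled 12-month rate: up to about 1.15 times the planned variance as a baseline row and 1.07 times as a single covariate (both at m = 4, k = 2, r = 0.8).

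**Simulation check (m = 0.3, k = 1, stable, 50 per arm).** SE was 0.153 for change, 0.121 for follow-up only and 0.119 with the 3-month covariate. The formula for change gives √(2 × 0.600/50) = 0.155.

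**Power.** For an assumed 50% ED reduction in that setting, at two-sided 0.05: 16% as planned, 23% with the 3-month covariate, 25% with 12 months of history as covariate.

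**The case against.** A reader might infer that both visit counts are sparse and that their baselines are mostly noise. The documents do not support this. Participants are Medicaid patients with an active prescription and a recent clinic visit, so non-ED visits need not be rare. At m = 2, k = 1 with stable rates, chance is only a third of the baseline variance, and subtracting it lowers the variance from 6.00 to 4.00. Even for ED visits the claim fails at m = 0.5, k = 3, where mk = 1.5.

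A reader might also blame the 3-month window itself. Most of the ED loss comes from the unadjusted contrast instead, and adjusting for the existing count needs no new data. Equal windows are a legitimate choice that fits the repeated-measures model without rescaling. A pooled 12-month baseline can do worse than the plan when rates drift and visits are frequent.

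It is also fair that every rate here is assumed, that the SAP makes these outcomes secondary, that power is low under every option, and that nothing says the change-score variance will be used to size the next trial. That the request could reach further back is inferred from its retrospective design, not stated.

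What remains is that the plan does not adjust for baseline visits in its main analysis, and adjustment lowered the variance in every scenario examined.

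**Conclusion.** The point holds as one about precision. The planned change contrast is less efficient than baseline adjustment for both visit counts. For ED visits it can be worse than discarding the baseline, provided mean times dispersion is below 1 (or below about 1.67 if personal rates drift with r = 0.8). For more frequent non-ED visits subtraction generally helps, but adjustment helps more. The estimated reductions of 29-44% (ED) and 14-39% (non-ED) depend on the assumed gamma-Poisson model, the rates listed and a linear analysis of the counts; the true figures depend on how stable personal rates are. There is no bias, because both arms share the same windows. Importance is modest in a pilot.

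**What to change.** In Protocol section 7 and SAP Data Analysis, keep the 3-month post-baseline count as the outcome for ED and non-ED visits, and test the arm effect with the pre-baseline count as a covariate in place of the change contrast. This step needs no extra data and gives most of the ED gain.

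In Protocol sections 5.1 and 9.2 and SAP Dataset, extend the look-back in the same end-of-study request to 6-12 months. Enter the last-3-month count and the earlier count as two separate covariates. Do not use a pooled 12-month rate as the baseline row of the GEE.

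The costs are wider approval and consent wording, more record data per person for about 100 people, and shorter histories for patients new to the health system. The SAP should state in advance how short histories are handled. If the wider request is not approved, the covariate change alone is still worth making.
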